8.2 Recording of Adverse Events

At each contact with the subject, the study team must seek information on adverse events by specific questioning and, as appropriate, by examination. Information on all adverse events should be recorded immediately in the source document, and also in the appropriate adverse

event section of the case report form (CRF). All clearly related signs, symptoms, and abnormal diagnostic, laboratory or procedure results should be recorded in the source document.

All adverse events occurring during the study period must be recorded. The clinical course of each event should be followed until resolution, stabilization, or until it has been ultimately determined that the study treatment or participation is not the probable cause. Serious adverse events that are still ongoing at the end of the study period must be followed up, to determine the final outcome. Any serious adverse event that occurs after the study period and is considered to be at least possibly related to the study treatment or study participation should be recorded and reported immediately.

8.3 Reporting of Serious Adverse Events and Unanticipated Problems

When an adverse event has been identified, the study team will take appropriate action necessary to protect the study participant and then complete the Study Adverse Event Worksheet and log. The sponsor-investigator will evaluate the event and determine the necessary follow-up and reporting required.

8.3.1 Sponsor-Investigator reporting: notifying the Mayo IRB

The sponsor-investigator will report to the Mayo IRB any UPIRTSOs and Non-UPIRTSOs according to the Mayo IRB Policy and Procedures.

8.3.2 Sponsor-Investigator reporting: Notifying the FDA

AEs that meet the criteria of serious, related to study drug, and unexpected as determined by the PI, qualify for reporting to the regulatory authorities (FDA). The Principal Investigator will assess all SAE's occurring during the study and evaluate for "unexpectedness" and relationship to study drug. The PI should complete and submit a voluntary MedWatch Report for events determined to meet the criteria as serious, study drug related and unexpected to:
<https://www.accessdata.fda.gov/scripts/medwatch/>.

8.4 Stopping Rules

Adverse events and serious adverse events, as defined in Section 8, will be monitored by the study team for patient safety. The study team will review the adverse events and determine if there is significant difference of adverse events and SAEs between the 2 arms. Review will occur frequently and summary of findings will be documented. If there is a clinically and statistically significant difference in adverse event and SAEs, the study team will consider placing the project on hold. IRB will be notified through the IRB electronic system if the study is placed on hold. The study team will formulate an appropriate plan of action to ensure patient safety. Such a plan may include, but is not limited to, protocol modifications, immediate termination of accrual, adjustments in management of previously enrolled participants continuing to undergo study interventions.

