Our preliminary data from a large insurance-claims database show that women with fibroids were more likely to continue use of LNG-IUS (62% at 6 months) than TXA (22% at 6 months) for the treatment of HMB; however, we were unable to ascertain reasons for discontinuation in either group (16). Accurately predicting which women with fibroids are optimal candidates for medical therapy is a key unanswered question of the Agency for Healthcare Research and Quality (AHRQ) evidence-based review and would have substantial impact on the clinical care for women with fibroids (17).

Thus, we propose a **randomized controlled trial (RCT)** to assess the **comparative effectiveness** of LNG-IUS to TXA for the **treatment of HMB in women with clinically-significant fibroids**. We will measure patient-reported outcomes recognized to be important to women with HMB and study the clinical factors (e.g. body mass index, age) and fibroid factors (e.g. size, location) that predict successful medical therapy.

After greater than 1 year of enrollment and randomization, we have found that we have a higher rate of drop outs in the TXA arm than expected. Nearly all participants in the TXA arm have dropped out (n=4) before 6 months participation due to various side effects. Clinically, we use this medication and do not receive the same reported side effects. Thus, we would like to evaluate the use of TXA in a population that has self-selected the use of the medication. **We will add an observational arm to the study for women who otherwise meet study criteria and select either TXA or LNG-IUS, but decline randomization.**

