4.4 Early Withdrawal of Subjects

4.4.1 When and How to Withdraw Subjects

Participants may be withdrawn from the study at any time prior to completion of the study for the following reasons:

- Safety issues including allergic or adverse reaction to either medication
- If the participant develops clinically significant anemia from on-going HMB, she will be offered different treatment options
- Displacement of LNG-IUS will require removal and participant may opt to withdraw from study or have a new device placed
- Participant decision to withdraw from study (withdrawal of consent)
- Unable to comply with the study protocol

There are no adverse effects from stopping either treatment suddenly. We will encourage the participant to complete the study end measures (clinical laboratories, ultrasound, exam) to provide useful information to provide their primary care or gynecological provider on the management of their HMB. This data will be useful to understand the treatment effect on the fibroids, bleeding, and well-being of the participants. If withdrawn from the study and not agreeable to the additional measures, we will use only data collected to that point. We will plan our recruitment to account for 20% attrition from the study so that individual participants will not require replacement.

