7.1 Sample Size Determination

Aim 1. The primary outcome variable will be the difference in MMAS score at 6 months between the treatment arms. Based on the ECCLIPSE trial, the observed effect size at 6 months for the MMAS total score was 0.58 standard deviations (8). In order for the proposed trial to

have 90% power to detect such a difference, we would need 64 patients per treatment arm. To allow for up to 20% loss to follow-up or incomplete data without the potential to carry-forward an MMAS score from an earlier assessment, we will enroll 80 patients per treatment arm. From our preliminary study of a large insurance-claims database, we found a 40% difference (62% vs. 22%) in continued use of the index medication at 6 months. Based on the sample size of 80 women per arm, we will have over 90% power to detect such a difference if it exists in the data from the proposed trial. These calculations are based on a two-sample t-test and chi-square test, respectively, assuming a type I error of 0.05 and a two-sided alternative hypothesis.

Aim 2. As described in Aim 1, we plan to enroll 80 patients in each treatment arm. Among these 160 patients, we anticipate that at least 80 patients will have intentionally discontinued treatment by the end of the study. Table 3 below summarizes the detectable hazard ratios for different factor scenarios with varying prevalence. Assuming that 50% of the study participants will have a BMI > 30 kg/m², this aim will have 80% power to detect an association between obesity and intentional discontinuation.

Table 2. Detectable hazard ratios with 80% power based on a two-sided logrank test with a type I error of 0.05	
Prevalence of factor	Among the 160 patients in both arms (assume 80 intentionally discontinue)
20%	2.19
30%	1.98
40%	1.90
50%	1.88

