For this study, the study treatment follow-up period is defined as 9 months after enrollment. Events occurring after this visit will be managed clinically. For women with a contraindication to LNG-IUS (e.g. a type I fibroid), we will recommend removal of the LNG-IUS at the 9-month visit to reduce risks.

Preexisting Condition

A preexisting condition is one that is present at the start of the study. A preexisting condition should be recorded as an adverse event if the frequency, intensity, or the character of the condition worsens during the study period.

General Physical Examination Findings

At screening, any clinically significant abnormality should be recorded as a preexisting condition. At the end of the study, any new clinically significant findings/abnormalities that meet the definition of an adverse event must also be recorded and documented as an adverse event.

Post-study Adverse Event

All unresolved adverse events should be followed by the sponsor-investigator until the events are resolved, the subject is lost to follow-up, or the adverse event is otherwise explained. At the last scheduled visit, the sponsor-investigator should instruct each subject to report, to the sponsor-investigator, any subsequent event(s) that the subject, or the subject's personal physician, believes might reasonably be related to participation in this study.

Abnormal Laboratory Values

A clinical laboratory abnormality should be documented as an adverse event if hemoglobin were to drop below 8.0 g/dL during treatment for HMB.

Hospitalization, Prolonged Hospitalization or Surgery

Any adverse event that results in hospitalization or prolonged hospitalization should be documented and reported as a serious adverse event unless specifically instructed otherwise in this protocol. Any condition responsible for surgery should be documented as an adverse event if the condition meets the criteria for an adverse event.

Neither the condition, hospitalization, prolonged hospitalization, nor surgery are reported as an adverse event in the following circumstances:

- Hospitalization or prolonged hospitalization for diagnostic or elective surgical procedures for a preexisting condition. Surgery should **not** be reported as an outcome of an adverse event if the purpose of the surgery was elective or diagnostic and the outcome was uneventful.

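### The 8.4 adverse-event comparison ignores unequal time at risk, and women withdrawn after a reaction lose their remaining month-3 and month-6 AE calls

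*Combined protocol and SAP*

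**What the plan says.** **The comparison.** Section 8.4 (Stopping Rules) states: "The study team will review the adverse events and determine if there is significant difference of adverse events and SAEs between the 2 arms". On timing it says only: "Review will occur frequently and summary of findings will be documented". It does not say whether counts, proportions or rates are compared, by which test, or at which dates. It mentions neither time on treatment nor time under observation. A difference that is significant both clinically and statistically leads the team to consider a hold. Under 8.5.1 the DSMB receives a summary of AEs.

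**Withdrawal.** Section 4.4.1 lists reasons for which a participant may be withdrawn from the study. One is "Safety issues including allergic or adverse reaction to either medication". The section has no separate status for a woman who stops treatment but stays in follow-up. Withdrawn women are encouraged to complete the end-of-study measures; for those who decline, "we will use only data collected to that point".

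**AE collection.** Table 1 schedules AE collection at months 3, 6 and 9. Its footnote 6 brings the month-9 column, AEs included, forward to the time of withdrawal. Section 4.4.2 seeks permission for a month-9 follow-up of withdrawn women that asks about AEs. Section 8.2 requires every AE in the study period to be recorded.

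**Expected persistence.** Section 7.1 plans on claims data: "we found a 40% difference (62% vs. 22%) in continued use of the index medication at 6 months", the higher figure being LNG-IUS. Section 1.1 reports that nearly all TXA participants so far (n=4) left before month 6 because of side effects.

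**The concern.** A comparison of women with an AE, or of AE counts per woman, reflects how often AEs occur only if the arms are at risk and observed for similar lengths of time. The protocol expects sharply different persistence, and two kinds of time then come apart.

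- *Time on treatment.* An AE that can arise only during use has less time to occur in the arm that stops sooner, even if every woman is followed to month 9.
- *Time under AE observation.* An AE that can arise at any time is missed if the woman has left the scheduled calls. Because 4.4.1 does not separate stopping treatment from leaving the study, women with reactions are the ones likely to lose those calls.

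Both effects favour the arm that women leave sooner, here expected to be TXA. This comparison is the basis that 8.4 gives for considering a hold.

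**Working it through.** **Inputs from the documents.** Continuation at 6 months S(6): TXA 0.22, LNG-IUS 0.62; 80 women per arm (7.1). Follow-up 9 months (8.1). Study attrition 20%, not split by arm (4.4.1, 7.1).

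**Assumptions not in the documents.** The shape of the stopping curve, the AE rates, the share of stoppers who leave AE collection, the share of stops caused by an AE, and a two-sided 0.05 test for 8.4.

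**1. The plan's own figure.** The documents give no exposure figure for AEs. With 80 per arm, the power for 62% against 22% is 0.9997, which agrees with the stated power of over 90%.

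**2. Time on treatment.** With a constant stopping rate, h = −ln S(6)/6:

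- TXA: 1.514/6 = 0.252 per month
- LNG-IUS: 0.478/6 = 0.0797 per month

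Mean months on treatment to time T = (1 − exp(−hT))/h:

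| T | TXA | LNG-IUS | Ratio |
|---|---|---|---|
| 3 months | 2.10 | 2.67 | 1.27 |
| 6 months | 3.09 | 4.77 | 1.54 |
| 9 months | 3.55 | 6.42 | 1.81 |

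At 80 per arm the 9-month row is about 284 against 514 woman-months. The model implies 71.7 + 40.9 = 112.6 stops by month 9, which is consistent with the plan's expectation of at least 80.

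Other shapes through the same 6-month points, to month 9:

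- Weibull, shape 0.5: 2.90 against 6.15, ratio 2.12
- Weibull, shape 2: 4.28 against 6.60, ratio 1.54
- Linear to month 6, then flat: 6(1+S)/2 + 3S = 4.32 against 6.72, ratio 1.56

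**3. Time under AE observation.** If a fraction f of stoppers also leaves AE collection, mean observed time = f × (time on treatment) + (1 − f) × 9:

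| f | TXA | LNG-IUS | Ratio |
|---|---|---|---|
| 100% | 3.55 | 6.42 | 1.81 |
| 75% | 4.92 | 7.07 | 1.44 |
| 50% | 6.28 | 7.71 | 1.23 |
| 25% | 7.64 | 8.36 | 1.09 |
| 0% | 9.00 | 9.00 | 1.00 |

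With the protocol's 20% attrition instead, equal arms give 8.07 months each (ratio 1.00). A split of 30% against 10% gives 1.13, and 40% against 0% gives 1.28.

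**4. AEs unrelated to stopping, at the extreme f = 100%.** With AE rate r per month, the proportion with a recorded AE = r/(r+h) × (1 − exp(−9(r+h))).

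- r = 0.05 in both arms: TXA 15.4%, LNG-IUS 26.6%.
- r = 0.05 for LNG-IUS and 1.81 × 0.05 = 0.090 for TXA: TXA 25.2%, LNG-IUS 26.6%, so the arms look alike.
- The same two rates acting and observed for the full 9 months, 1 − exp(−9r): TXA 56%, LNG-IUS 36%, with power 0.70 at 80 per arm.

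**5. AEs that cause the stop and are recorded at withdrawal.** If a share q of stops is AE-caused, the proportion = q × (1 − exp(−9h)):

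| q | TXA | LNG-IUS | Power at 80 per arm |
|---|---|---|---|
| 25% | 22% | 13% | 0.36 |
| 50% | 45% | 26% | 0.73 |
| 100% | 90% | 51% | >0.99 |

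Here the TXA excess shows.

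**The case against.** The strongest objection is that the reaction that makes a woman stop is itself an AE. Table 1 footnote 6 and section 8.2 mean it should be recorded. Step 5 shows that such AEs would point to a TXA excess, and the team did notice the pattern at n=4. This stands, and it confines the understatement to other AEs. It does not remove it, because 8.4 does not name AE-caused discontinuation as something to compare.

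Second, 4.4.1 is permissive, stopping treatment is not the same as leaving the study, and 4.4.2 seeks a month-9 contact. The 62% and 22% are drug persistence in claims data, for which "we were unable to ascertain reasons for discontinuation in either group"; they are not withdrawal rates. This also stands for observation time, as step 3 shows. It does not touch time on treatment, because any stop ends use whatever its reason.

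Third, reviews before month 9 face a smaller imbalance. That is right, although the ratio is already 1.27 at 3 months and 1.54 at 6.

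Fourth, 8.4 does not say that it compares per woman, it also requires clinical significance, and the DSMB sees an AE summary. All true; but with no measure named, nothing brings time at risk into that review.

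Fifth, TXA is taken for at most 5 days per cycle, so a month on TXA is not the same kind of exposure as a month with the device in place. This limits the per-month scale and is a reason to show it beside the per-woman scale rather than alone.

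A reader might also infer that 4.4.1 contradicts 8.1, which says "All unresolved adverse events should be followed by the sponsor-investigator until the events are resolved". It does not. That sentence concerns AEs already found and goes on to except loss to follow-up, and the data-to-that-point rule applies only to women who decline further measures.

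**Conclusion.** The point holds in a limited form. Section 4.4.1 allows withdrawal from the study where only treatment need stop, the remaining interim AE calls are then lost, and 8.4 compares arms without regard to time at risk. Time on treatment would differ about 1.8-fold by month 9 (1.5 to 2.1 by shape of the stopping curve), given the protocol's persistence figures. AE-observation time would differ less: 1.09 to 1.44 if 25% to 75% of stoppers leave collection.

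A reader might infer that 8.4 sets 3.6 months of AE collection against 6.4 and so hides a TXA rate about twice as high. The documents do not support that. Those are months on treatment, and they equal months of AE collection only if every stopper leaves it. The masking in step 4 also assumes AEs independent of stopping, whereas the recorded AE behind a stop works in the other direction.

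The conclusion rests on claims persistence carrying over to this trial and on assumed curve shapes and AE rates. The four TXA drop-outs agree in direction but are too few to size it.

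**What to change.** - **Section 4.4.1:** for data collection, separate discontinuation of treatment from withdrawal from the study. Keep the scheduled month 3, 6 and 9 AE contacts for a woman who stops treatment unless she withdraws consent. This leaves the clinical decision to stop treatment as the protocol has it.
- **Section 8.4 and the DSMB summary:** show AEs and SAEs by arm both per woman and per person-month on treatment, and show discontinuations caused by an AE by arm.

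The cost is protocol wording, one more table column and one more row. The contacts are already in Table 1, and stop dates are needed anyway because duration of use is a primary endpoint (3.2). The downside is that per-month rates suit front-loaded insertion events and intermittent TXA dosing less well, which is why both scales are shown.

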7.2 Statistical Methods

Descriptive Statistics

Standard descriptive statistics will be generated for measurements at baseline, 3, 6, and 9 months, including mean, median, standard deviation (SD), and interquartile range (IQR) for continuous variables and counts and percentages for categorical variables.

Handling of Missing Data

Last value carry forward (LVCF) methods will be investigated to accommodate drop-outs.

Primary Hypothesis: A user-independent medical therapy (LNG-IUS) will result in better patient reported outcomes and longer use compared to self-administered medication (TXA)

Statistical analysis: The distribution of each of the continuously scaled outcome measures (MMAS total score, PBLAC score, ferritin level, hemoglobin level, UFS-QOL scores, and Rand

SF-36 composite scores) will be graphically evaluated and logarithmic transformations will be applied if the distributions are skewed in order to obtain more normally distributed distributions. At 3, 6, and 9 months separately, each of the continuously scaled outcomes will be compared between treatment arms based on fitting separate linear regression models. In addition, separate analysis of covariance (ANOCOVA) models will be fit to compare the measures between the two treatment arms after adjusting for baseline levels. The cumulative incidence (CI) function will be used to estimate the cumulative proportion of patients by time t who have intentionally discontinued treatment due to the desire or need to stop or switch treatment, after accounting for the competing risk of LNG-IUS expulsion and censoring all other participants at their date of last follow-up or end of study. Likewise we will also estimate the CI of expulsion among the LNG-IUS treatment arm. The CI estimates for intentional discontinuation over the entire 9 months of follow-up will be compared between treatment arms using the methods developed by Gray (34). All analyses will be performed based on the intention to treat principle and calculated p-values will be based on two-sided hypothesis tests. P-values less than 0.05 will be considered statistically significant. Statistical analyses will be performed using the SAS version 9.4 software package and packages in R (Version 3.1.1).

Secondary Hypothesis 1: Large fibroid size will limit the effectiveness of LNG-IUS compared with TXA; elevated BMI predicts higher success with LNG-IUS over TXA.

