8.5.1 Internal Data and Safety Monitoring Plan

We will utilize the Mayo Clinic Department of Surgery Data Safety Monitoring Board (DSMB) for oversight of the study. Adverse events (AE) will be monitored by the study team, who has primary responsibility for attribution of the AE to the study. Events that prompt the activation of the protocol-specific stopping rules will be reviewed by the study team, during which time study accrual may be halted. The team will formulate a plan of action to ensure patient safety and forward the plan to the DSMB. The DSMB will review the action plan and recommend approval or provide recommendations to the IRB. A summary of all AEs will be provided to the DSMB for review and on-going study approval.

9 Data Handling and Record Keeping

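### The written trigger for considering a safety hold (section 8.4) needs statistical as well as clinical significance, a condition that a real imbalance in infrequent serious events would usually not meet

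*Combined protocol and SAP*

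**What the plan says.** Section 8.4 asks the study team to review adverse events and "determine if there is significant difference of adverse events and SAEs between the 2 arms". On timing it says only "Review will occur frequently and summary of findings will be documented". The trigger is: "If there is a clinically and statistically significant difference in adverse event and SAEs, the study team will consider placing the project on hold". Section 8.4 names no test, significance level, event count or adjustment for repeated looks.

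The only significance level in the plan is in section 7.2, in the analysis of the primary hypothesis: "P-values less than 0.05 will be considered statistically significant", where "calculated p-values will be based on two-sided hypothesis tests".

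Section 8.5.1 builds on the same rule: "Events that prompt the activation of the protocol-specific stopping rules will be reviewed by the study team". Accrual may be halted during that review, and the team's action plan then goes to the DSMB. Separately, the same section has the DSMB receive a summary of all adverse events as part of continuing approval, with no schedule stated.

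On numbers, section 7.1 says "we will enroll 80 patients per treatment arm". Section 1.1 reports, after more than a year of enrolment: "Nearly all participants in the TXA arm have dropped out (n=4) before 6 months participation due to various side effects".

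**The concern.** Statistical significance is a demanding condition when events are few. The team could see an imbalance in serious events that it judges clinically important, and the written rule would still not be met because the p-value is above 0.05. The accrual halt and the action plan sent to the DSMB are tied to activation of this rule, so they would not be set in motion by it either. For safety monitoring the costs of error are lopsided. A false alarm leads only to a discussion, because the rule says a hold will be considered. A missed signal leaves women exposed and accrual open.

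Leaving the test unspecified adds to the problem: the same event counts can meet the condition under one usual test and fail it under another.

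**Working it through.** **Inputs from the plan.** 80 women per arm (7.1); two-sided 0.05 (7.2, borrowed here because 8.4 gives no level of its own); review at unspecified frequent intervals (8.4). The plan gives no expected SAE rate, so every rate below is my assumption.

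**What the sample size was built for.** With an effect of 0.58 SD, 90% power and two-sided 0.05, the normal approximation gives n = 2(1.960 + 1.282)² / 0.58² = 62.5, so 63 per arm. The t-test gives 63.4, so 64, as stated. Allowing for 20% loss, 64 / 0.80 = 80. The plan's figure reproduces. It concerns MMAS, with a power check on continued use; safety plays no part in it.

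**Event splits needed.** For 0 v k events with n women per arm, the two-sided Fisher p-value is 2·C(n,k) / C(2n,k). The uncorrected chi-square statistic is k / (1 − k/2n) on 1 degree of freedom.

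| Women per arm | Split | Fisher p | Chi-square p |
|---|---|---|---|
| 80 | 0 v 4 | 0.120 | 0.043 |
| 80 | 0 v 5 | 0.059 | 0.023 |
| 80 | 0 v 6 | 0.028 | 0.013 |
| 80 | 1 v 7 | 0.064 | 0.030 |
| 80 | 1 v 8 | 0.034 | 0.016 |
| 20 | 0 v 4 | 0.106 | 0.035 |

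Example at 80 per arm, 0 v 5: Fisher is 2·C(80,5) / C(160,5) = 0.0586; the chi-square statistic is 5 / (1 − 5/160) = 5.16, p = 0.023. The verdict on this split depends on a test the plan does not name.

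**Chance that one look gives p < 0.05.** This is the sum of the two binomial probabilities over all splits with p < 0.05 (Fisher / uncorrected chi-square).

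| Assumed SAE rates | 40 per arm | 80 per arm |
|---|---|---|
| 1% v 5% | 1% / 10% | 11% / 30% |
| 1% v 6% | 2% / 15% | 20% / 40% |
| 2% v 6% | 1% / 11% | 11% / 22% |
| 2% v 8% | 5% / 22% | 26% / 39% |
| 2% v 10% | 11% / 34% | 44% / 57% |
| 5% v 15% | 18% / 35% | 48% / 57% |
| 2% v 15% | 36% / 63% | 82% / 88% |

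The first four rows give the ranges 11-26% / 22-40% at 80 per arm and 1-5% / 10-22% at 40. Rarer events do worse: 1% v 3% gives 2% / 10% at 80 per arm. Common events do better: an assumed AE imbalance of 10% v 40% gives 85% (Fisher) at 40 per arm and 99% at 80.

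**Repeated looks.** I simulated a look after every 10 women per arm (8 looks, each at an unadjusted 0.05, 100,000 runs). The chance of ever meeting the condition is 12% / 35% for 1% v 5%, 13% / 31% for 2% v 6%, and 29% / 49% for 2% v 8%. The same looks give a false-trigger rate of about 10% / 17% for an AE at 30% in both arms.

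**At the size reported in section 1.1.** The arm size is not stated; if it was about 5, Fisher needs 4 v 0 (2·C(5,4) / C(10,4) = 0.048) and chi-square needs 3 v 0 (3 / (1 − 3/10) = 4.29, p = 0.038).

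**The case against.** Four points count on the other side.

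1. **Choice of test.** The only test the plan names for comparing proportions is chi-square, in the power calculation in 7.1. Under it, 5 v 0 of 80 and 4 v 0 of 20 both reach significance. This stands: no particular small split can be said to fail the rule in general. Over the assumed low rates, though, the chance stays below one half under either test, even with eight looks.

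2. **Significance is not always out of reach.** A reader might infer that the condition is practically unattainable. The documents do not support that. The rule covers all adverse events, many of which may be common, and very large SAE imbalances near full enrolment would usually meet it. At 2% v 10% or 5% v 15% with 80 per arm, the chance is near even.

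3. **'If' is not 'only if'.** A reader might infer that no hold is possible without p < 0.05, or that safety oversight as a whole fails. Neither follows. Section 8.4 describes one circumstance for considering a hold and bars no others. Section 1.1 reports a design change after the TXA drop-outs and mentions no significance test.

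4. **Other routes exist.** The DSMB sees a summary of all adverse events (8.5.1), SAEs are regularly assessed (8.5), the IRB and FDA receive reports (8.3.1, 8.3.2), and individuals can be withdrawn for safety (4.4.1). A harm common to both arms lies outside a between-arm comparison but could surface through these. This also stands. None of these provisions, however, sets another criterion for a hold, and the DSMB summary has no stated schedule.

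**Conclusion.** The concern holds for the written trigger, not for safety oversight as a whole. As worded, a difference judged clinically important but not statistically significant does not meet the rule, and the accrual halt and action plan in 8.5.1 are linked to that rule. For infrequent serious events, and for any early look at them, the significance condition would usually not be met. The sizes rest on assumed SAE rates, independent binomial counts, equal arms and the 0.05 level borrowed from 7.2. They weaken as the imbalance grows and do not carry over to common adverse events. This is a worthwhile and cheap correction of wording.

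**What to change.** In section 8.4, remove statistical significance as a necessary condition. A between-arm difference judged clinically important should be enough to open the hold discussion and to notify the DSMB. Report the exact confidence interval for the difference in event proportions alongside, as supporting information only. Align section 8.5.1 so that its reference to activation of the stopping rules matches the new wording. Any clinical threshold, including one for harm common to both arms, stays with the investigators and the DSMB.

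The cost is a change to a few sentences and more occasions on which a hold is discussed. Because the rule commits the team only to consider a hold, each such occasion costs little. The sample size and the efficacy analyses are not affected.
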